## 6. DATA COLLECTION AND VARIABLES

Core analyses will employ data collected during routine clinical care and hospital operations. There will be no direct patient contact for collection of identifiable data or specimens.

#### 6.1 Data Collection

Intermountain's Enterprise Data Warehouse (EDW) is a centrally-managed, well-curated, and accessible database linking system-wide clinical, billing, laboratory, and other data. Eligible patient subjects will be identified by project data managers from EDW data, who will generate a dataset specific to the proposed study by linking EDW data to additional data abstracted from the electronic health record. Manual chart review and direct queries to bedside clinicians will be employed as needed to supplement electronically-available data. This encounter level data will be linked to additional data on hospital characteristics, physician and nurse staffing. Long-term mortality data will be obtained through a preexisting linkage to Utah state death records and/or the federal Social Security Death Index. Encounter data will be linked to data on race, ethnicity, and hospital admissions (admit date, type, diagnoses, and costs) stored in the Utah Population Databank. We will employ a preexisting linkage to Utah State death records Security Death Index for mortality ascertainment.

# 6.2 Anonymous Data Collection For Protocol Development and During Live Code Sepsis Activation

The study team will receive notification of Code Sepsis activations. As part of the study operational process, ED clinical leadership and study personnel will directly observe a convenience sample of these events to anonymously record protocol parameters, including team composition and process completion times. In addition, a convenience sample of intervention hospital patients (<10) with sepsis may be observed during the pre-Code Sepsis implementation phase to understand care processes involved in sepsis care. No identifying information about the patient or clinical team will be recorded.

#### 6.3 Active Follow-Up for Patients Undergoing Code Sepsis

Via the electronic medical record, a member of the study team will actively monitor Code Sepsis activation patients every 1-3 days until hospital day #7. There will be no direct patient contact.

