#### 10.2.3 Adverse event monitoring

The PI will review potential adverse events monthly for patients for whom the Code Sepsis protocol was activated during the patient's ED visit. The PI will also review within 72 hours of identification any potential anaphylaxis cases occurring within 24 hours of ED antibiotic initiation in Code Sepsis patients. Adverse events will be monitored via review of the medical record for the first 3 days after Code Sepsis activation or until hospital discharge, whichever occurs first, regardless of the investigator's opinion of causation. Thereafter, serious adverse events are not required to be collected unless routine clinical care monitoring or the PI believes that the event was possibly, probably, or definitely to the Code Sepsis protocol.

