#### 10.3 Adverse Event and Serious Adverse Event Reporting

We emphasize in AE reporting for this study that the intervention under study is an expedited bundling of established elements of clinical care. Study-specific clinical outcomes of sepsis and ED clinical care are exempt from adverse event reporting *unless* the investigator deems the event to be related to the administration of study drug or the conduct of study procedures (or of uncertain relationship). The following are examples of events that will be considered routinely recorded clinical outcomes:

- Death not related to study procedures.
- Adverse drug reaction (excluding anaphylaxis associated with antibiotic administration) not related to study procedures
- Secondary and healthcare associated infections
- Persistent or progressive organ failure

• Prolonged hospitalization

The PI will report to the ISM within 72 hours of identification all AEs that are serious and possibly, probably, or definitely related to study procedure (or of uncertain relationship) or are unexpected. If the ISM concurs with the PI's assessment, the AE will be reported to the IRB within 7 business days. Other AEs will be reviewed by the PI on a monthly basis and reported in aggregate to the ISM on a quarterly basis. A summary report on all adverse events will be submitted to the IRB during annual recertification as per IRB guidelines. Good Clinical Practice will be followed for conduct of the study.

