#### 10.5.1 Safety Monitoring Procedures

- 1. Since this research examines implementation of a method to deliver clinical standard-of-care therapies in a more efficient, expeditious, and coordinated manner, the foundation for safety monitoring for this study is the routine quality assurance monitoring of the study hospital's Emergency Department. This quality assurance activity includes review of incident reports for clinical adverse events. The ED physician who serves as site medical director and currently has lead responsibility for monitoring of care quality and safety in each study ED. The study team will be in monthly contact via telephone or email with the ED medical director overseeing quality assurance efforts at the intervention hospital to identify potential concerns possibly, probably, or definitely related to Code Sepsis implementation. If necessary, comparisons to control hospital EDs will be performed on the basis of reports from their medical directors.
- 2. Specific to study procedures, all Code Sepsis activations will be individually evaluated. The PI will review all Code Sepsis activations on a monthly basis. AEs will be reported to the ISM in aggregate on a quarterly basis. The PI will report to the ISM within 72 hours of identification all AEs that are serious and possibly, probably, or definitely related to study procedure (or of uncertain relationship) or are unexpected. The ISM and PI together will reach consensus on the ultimate characterization of these possible serious adverse events (SAEs). If disagreement persists after discussion between the ISM and PI, the ISM will make the final decision about the status of the possible SAE. SAEs will be reported to the IRB within 7 business days.
- 3. If required by NIH or other governing bodies, or based on issues observed during trial conduct, we will convene a Data Safety Monitoring Board (DSMB) of clinical experts and members with

expertise in implementation trials with assistance from the Utah Center for Clinical and Translational Science.

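### Chart review of activated patients runs to hospital day 7, but causation-blind event collection ends at 3 days or discharge, and the collection trigger after that is narrower than the rule for reporting to the safety monitor

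*Protocol*

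**What the plan says.** Protocol 6.3, in the data collection chapter, says a member of the study team "will actively monitor Code Sepsis activation patients every 1-3 days until hospital day #7", through the electronic medical record and without patient contact. It gives no purpose and does not say what is written down.

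Protocol 10.2.3 sets the adverse-event window. Events are found by record review "for the first 3 days after Code Sepsis activation or until hospital discharge, whichever occurs first", whatever the investigator thinks of causation. The section continues: "Thereafter, serious adverse events are not required to be collected unless routine clinical care monitoring or the PI believes" the event to be possibly, probably or definitely related to the protocol.

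Protocol 10.3 and 10.5.1 set the reporting rule. Within 72 hours of identification the PI tells the safety monitor of "all AEs that are serious and possibly, probably, or definitely related to study procedure (or of uncertain relationship) or are unexpected". No day limit is attached. Other events go to the monitor in a quarterly aggregate, and the IRB receives an annual summary. Section 10.3 also states that "Study-specific clinical outcomes of sepsis and ED clinical care are exempt from adverse event reporting", unless the investigator deems them related or of uncertain relationship. Section 10.5.1 adds: "The PI will review all Code Sepsis activations on a monthly basis".

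**The concern.** The same patients and the same source are reviewed over two periods of different length. The periods are also counted differently: hospital days in 6.3, days since activation in 10.2.3. Someone opening a chart on day 5 cannot tell from the protocol what to log.

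What is at stake is the information that reaches the safety monitor. Under 10.5 the monitor can end the study on a safety signal, and under 10.5.1 the monitor decides when the two disagree on a possible serious event. That safeguard works only for events that were collected. After the 3-day window, an opinion on causation comes before collection and so before the monitor's view. Nothing requires the quarterly counts to state the window they cover.

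**Working it through.** The plan states no figure to reproduce. The check is a comparison of rules plus a count of days.

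**Days.** Assume activation on hospital day 1 and count calendar days.
- Section 10.2.3, causation-blind: days 1-3 at most.
- Section 6.3, chart review: days 1-7.
- Difference: 7 - 3 = 4 days (days 4-7). If 3 days means a full 72 hours running into day 4, the difference is about 3 days.
- A patient discharged by day 3 has no in-hospital gap.

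**Patients.** Protocol 7.3 plans for 1,650 sepsis patients a year at the intervention ED, with activation in 30% during phase #3: 0.30 x 1,650 = 495. Activated patients without sepsis, and activations during phase #2, fall under the same rules, but their numbers are not given.

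**Rules for a serious event on days 4-7.** The attribution scale in 10.2.1 lists uncertain relationship as its own category, separate from probably or possibly related. It therefore cannot simply be read into the 10.2.3 trigger.

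| Serious event, days 4-7 | Must be collected under 10.2.3? | 72-hour report under 10.3 / 10.5.1? |
|---|---|---|
| Believed possibly, probably or definitely related | Yes | Yes |
| Uncertain relationship | Not required | Yes |
| Unexpected, believed unrelated, not an exempt routine outcome | Not required | Yes |
| Expected, believed unrelated, not exempt | Not required | No; quarterly aggregate only |
| Exempt routine outcome, deemed unrelated | Not required | No |

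The second and third rows are where the rules conflict. The reporting rule can be parsed in two ways: serious and either related or unexpected, or else both serious and related, or unexpected. A serious, unexpected event is reportable under both.

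**Which outputs are touched.** The safety outcomes in Protocol 3.7.2 and the SAP safety table come from discharge codes, stool tests, antibiotic records and adjudicated infection status. Long-term mortality comes from death-record linkage (Protocol 6.1). None uses either window. That leaves the event tallies for activated patients that go to the safety monitor and the IRB.

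**The case against.** The strongest reply is that 6.3 is not an adverse-event rule. It never mentions adverse events, and its chart checks could serve other items in 6.5, such as culture results or antibiotic use. Section 10.2.3 alone defines the collection window, so both sections can be followed as written. This stands in part: a reader might infer that 6.3 and 10.2.3 flatly contradict each other, and they do not. It does not dispose of the point. Section 8.3 promises review of the records of all activations for adverse effects and gives no window. Section 10.5 directs safety monitoring at activations. No outcome in either document is defined at hospital day 7. Safety follow-up is the natural reading of 6.3, though not the only one. The conflict between 10.2.3 and 10.3/10.5.1 does not depend on that reading.

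A second reply is that filtering by relatedness is deliberate for an intervention that bundles established care. Section 10.3 exempts unrelated death, organ failure, prolonged stay and secondary infection on any day, and the definition of serious adverse events in 1.2 already builds in relatedness. This also stands. It limits the number of events affected and means that aligning the windows would not remove the reporting filter. But 10.3 withholds the exemption from events of uncertain relationship, which are among those 10.2.3 leaves out after day 3.

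Third, monthly PI review has no day limit and could pick up such events. It could, but 10.2.3 still does not require them to be logged.

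**Conclusion.** The point holds as an unreconciled mismatch between 6.3 and 10.2.3, together with a real gap between what 10.2.3 requires to be collected and what 10.3 and 10.5.1 require to be reported. For a patient still in hospital it covers 4 of the 7 reviewed days, or about 3 on the 72-hour reading. This assumes activation on hospital day 1.

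Three stronger readings are not supported.
- That serious events on days 4-7 go unrecorded in general: those believed at least possibly related are still collected.
- That more than half of serious events are lost because 4 of 7 days fall outside the window: the documents give no event rate, timing or length-of-stay distribution, acute drug reactions may well cluster early, and many events are exempt on any day. No event count can be derived.
- That the trial's safety results depend on which section is followed: the prespecified safety outcomes and mortality do not use either window.

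It is worth correcting because the affected tallies are what the safety monitor sees during the trial.

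**What to change.** Reconcile 6.3, 10.2.3, 10.3 and 10.5.1:
- State in 6.3 what the review to hospital day 7 records, and cross-reference 10.2.3.
- Use one clock and one window in both sections.
- Log every serious event found in the chart reviews already planned to hospital day 7, whatever the opinion on causation. Keep the 10.3 exemptions as a rule about reporting, and say that they do not limit what is logged.
- Label each quarterly count with the window it covers.

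At minimum, extend the post-window trigger in 10.2.3 to serious events that are of uncertain relationship or unexpected, so that everything 10.3 and 10.5.1 make reportable must also be collected.

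The cost is a wording amendment across the four sections and somewhat more events logged from charts already being opened. No additional chart review is needed.

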#### 6.4 Protected Health Information

Protected health information including subject encounter codes, medical record numbers, birthdates, encounter event date and times, address, and social security number will be collected during the electronic query to allow manual chart abstraction and manual review of electronic record for data completion and verification.

#### 6.5 Variables/data elements

- Patient medical record number(s)
- Patient encounter ID code
- Hospital/facility
- Date of birth
- Age
- Sex
- Race

- Ethnicity
- Marital status
- Preferred language
- Insurance status/type
- Address/zip code (for determination of residence at a nursing facility or other long-term care facility and estimation of socioeconomic status)
- Social Security Number (to assist matching of encounter data to Social Security Death Index and Utah state death records)
- ED disposition
- Hospital disposition
- Date/time of all events related to ED visit and hospitalization (e.g. ED arrival & departure, hospital admission & discharge)
- Date/time antibiotics administered
- Antibiotic utilization
- APACHE II score
- APACHE IV score
- Acute physiology score
- Charlson index
- Elixhauser index
- SOFA score
- Baseline SOFA score over preceding 10 years
- Source of admission (e.g. home, SNF, LTAC, outside hospital)
- Source of infection
- Clinician infection determination, patient illness severity, sepsis status, and agreement with Code Sepsis activation
- Sepsis presence/absence
- Culture results
- Admission diagnosis
- Mode of arrival to ED
- ED triage data including triage acuity score
- Resident involvement in ED care
- Results of all laboratory testing
- Date/time of all laboratory testing
- ED length of stay
- ED vital signs
- ED medications
- ED interventions/procedures
- Date/time, elapsed time, and type of ED events including provider interaction, room placement, disposition
- Date/time of diagnostic testing, vasopressor initiation and other interventions, and management
- Date/time of interventions
- Date/time of blood or body fluid cultures
- Discharge diagnosis and procedure codes
- Billing diagnosis and procedure codes
- Diagnosis-related group
- Hospital length of stay

Code Sepsis I protocol Version 3.0

- In-hospital mortality
- Long-term mortality (e.g. 30d, 90d and 1y mortality)
- Healthcare charges
- ED patient census
- Number of ED beds
- ED patient flow (including counts of patient arrivals, boarding, and admissions)
- Attending physician ED staffing
- Nurse staffing
- Trauma registration status
- Allergies
- Adverse drug reaction events and date/time
- Code Sepsis team activation (Y/N)
- Code Sepsis activation date/time
- Code Sepsis care process completion date/times
- Code Sepsis team function
- Code Sepsis team composition (by role)
- Code Sepsis process adherence

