# 4. STUDY POPULATION AND ENROLLMENT

#### 4.1 Setting

Intermountain Healthcare (hereafter "Intermountain") is a nonprofit health system based in Salt Lake City, Utah with 23 hospitals in Utah and Idaho. Code Sepsis implementation will occur in a teaching ED (IMC, my "home" hospital) providing 89,000 visits annually (2.8% with clinical sepsis) for an economically and ethnically diverse population of 1.1 million in Salt Lake County, Utah plus referrals

from Wyoming, Nevada, and Idaho. To avoid spillover effects, concurrent control data will be electronically abstracted from two Intermountain EDs (Utah Valley Hospital and Dixie Regional Medical Center) staffed by other physician groups (Table 1).

Table 1. Study hospital characteristics

	, ,			
Site	Description	Hospital beds	ED beds	Annual ED visits
IMC	Tertiary/teaching	472	56	89,000
Utah Valle	ey Regional referral	395	28	49,000
DRMC	Regional referral	321	35	65,000

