# Inclusion/exclusion criteria

Cohort	Inclusion	Exclusion	Cohort eligibility indicator variable*
ED sepsis cohort (primary analysis cohort)	
 
(1) Age ≥18 years
 
(2) Arrival to an intervention or control ED during study period
 
(3) Met all Sepsis-3 criteria in the ED
 
Acute organ failure in the ED defined by SOFA score while in the ED ,≥2 points above baseline
 
Suspected or confirmed infection while in the ED, based on having both: 
 
i. Administration of ,≥1 IV or IV-equivalent antibiotics while in the ED for suspected infection (i.e. antibiotics not given for prophylaxis)
 
ii. Collection of ,≥1 body fluid cultures while in the ED
 
 
 
	
 
Trauma patient
 
Subsequent eligible ED visit with sepsis after first eligible encounter during an analysis window
 
	cohort_sepsis
All adult ED patients cohort	
 
(1) Age ≥18 years
 
(2) Arrival to an intervention or control ED during study period
 
	
 
Trauma patient
 
Received antibiotics within 6 hours prior to study ED arrival
 
Subsequent eligible ED visit after first eligible encounter during an analysis window
 
Left ED without evaluation or treatment
 
	cohort_all
Sepsis high-risk cohort	
 
Age ≥18 years
 
Arrival to an intervention or control ED during study period
 
First recorded temperature ≥38.0°C
 
First-recorded vital sign data meets ≥2 of:         
 
a. Systolic blood pressure <90 mmHg
 
b. Glasgow Coma Scale (GCS) score <15
 
c. Respiratory rate ≥22 breaths/min or oxygen saturation <85%
 
 
 
	
 
Trauma patient
 
Received antibiotics within 6 hours prior to study ED arrival
 
Subsequent eligible ED visit after first eligible encounter during an analysis window
 
Left ED without evaluation or treatment
 
	cohort_risk

Cohort	Inclusion	Exclusion	Cohort eligibility indicator variable*
Sepsis	(1) Age ≥18 years	(1) Trauma patient	cohort_mimics
mimic	(2) Arrival to an intervention or control ED during study period	(2) Received antibiotics	

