limited in that it only considers the control and treated groups during the pre-implementation phase. If the pre-test of parallel trends assumption fails, then we will weight the gamma regression model with propensity scores. As demonstrated by Stuart *et. al*, this will balance the covariates amongst the four study groups defined by their treatment status as well as time (pre vs post). We will leverage the covariate balancing propensity score (CBPS) library in R to generate propensity scores. This weighting approach can recover treatment effects in that it allows for adjustments due to observed baseline covariates that differ either across groups or over time. Covariates that will be used in generating propensity scores will include age; sex; weighted Elixhauser comorbidity score; English language preference; first-available heart rate, temperature, systolic blood pressure, and respiratory rate; acute physiology score; ED arrival at nightime (10 pm to 6:59 am), ED arrival on weekend (midnight Saturday to 11:59 pm Sunday), SARS-CoV-2 test result (positive, negative, or not performed during ED-associated hospitalization or within 14 days preceding ED arrival); and insurance type. For analyses involving a cohort of patients with sepsis, propensity score covariates will additionally include arrival to ED via ambulance; presentation from a long term care facility; serum lactic acid level checked and ≥2 mmol/dL; ED SOFA score; and ED-diagnosed infection source.

In order to account for the right skew known to exist in door-to-antibiotic time we will use generalized linear gamma regression to estimate the DID. Evaluation of secondary outcomes will employ an analogous approach using multivariable linear, Poisson, logistic, or gamma regression as appropriate. Data from the wash-in phase will be excluded from DID analyses. All multivariable models will be adjusted for demographic and clinical parameters with known or plausible associations with both outcomes and treatment hospital, presentation before or after Code Sepsis implementation, and/or Code Sepsis activation as well as select precision variables as detailed below. Analyses for secondary, safety, and heterogeneity of treatment effect outcomes will not be adjusted for multiple comparisons and will therefore be considered hypothesis generating.

Statistical significance will be set to p < 0.05. All analyses will be conducted with R.

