#### Primary and secondary outcome analysis covariates

Variables listed below will be included in multivariable adjusted analyses for primary and secondary outcomes listed above. Variables are also included in any associated subgroup and sensitivity analyses for these outcomes. For heterogeneity of treatment effect analyses, where continuous variables are categorized or dichotomized, the corresponding adjustment variable will also be categorized analogously in the adjustment model and for creation of the interaction term.

- Age (age, continuous)
- Female sex (sex, binary)
- Presentation from a long-term care facility (snf, binary)
- Weighted Elixhauser comorbidity score (elixhauser\_vw, continuous)
- Arrival to ED via ambulance (arrival\_mode, binary)
- English is preferred language (english\_preferred\_yn, binary)
- First-available temperature in ED (vs\_temp\_cat, categorical, reference group = 1 [temp 36-38°C])
- First-available systolic blood pressure in ED (**vs\_sbp**, continuous)
- Acute physiology score (aps\_24h, continuous)
- ED SOFA score (**sofa\_ed**, continuous)

• ED-diagnosed infection source (**source\_ed\_final\_simpler**, categorical, reference group = 1 [pneumonia])

**Figure 2.** Adjustment variables for primary & secondary multivariable analyses. The primary exposure is intervention ED arrival post-intervention and the primary outcome is door-to-antibiotic time. White symbols indicate potential confounders or precision variables included in the multivariable model, gray symbols represent an unobserved variable, and blue symbols (other than the outcome) represent an ancestor of outcome not included in the multivariable model.

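### The plan collects outside-hospital origin, but no primary-outcome analysis uses it, so a change in transfer share that differs from the control EDs could enter the difference-in-differences estimate

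*Protocol*

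**What the plan says.** Protocol 6.5 (Variables/data elements) lists "Source of admission (e.g. home, SNF, LTAC, outside hospital" among the items to be collected. The SAP's covariate list for primary and secondary outcomes has two terms that bear on how or from where a patient came: "Presentation from a long-term care facility (snf, binary", and ambulance arrival as a binary variable. It also has age, sex, Elixhauser score, language, first temperature, first systolic pressure, acute physiology score (APS), ED SOFA and infection source.

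The fallback propensity weights, used if the parallel-trends pre-test fails, add for sepsis cohorts "arrival to ED via ambulance; presentation from a long term care facility; serum lactic acid level checked" and other clinical items. They contain no transfer term. Transfer is also absent from the SAP's directed acyclic graph, its predefined subgroups and its sensitivity analyses.

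The SAP's rule for choosing covariates is that they have "known or plausible associations with both outcomes and treatment hospital, presentation before or after Code Sepsis implementation", or with activation of the protocol.

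In the SAP's inclusion/exclusion table, the primary sepsis cohort excludes only trauma and repeat visits. The criterion "Received antibiotics within 6 hours prior to study ED arrival" is listed for the other three cohorts but not for this one. Protocol 4.1 describes the intervention ED as a tertiary teaching site serving a "population of 1.1 million in Salt Lake County, Utah plus referrals" from three other states. Table 1 there describes both control hospitals as regional referral sites.

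**The concern.** For a patient sent from another hospital, the door-to-antibiotic clock starts at the study ED, after assessment elsewhere. The interval then reflects a different process from that of a first presentation. It may be shorter because the diagnosis is already made, or longer because a dose has already been given.

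A difference-in-differences design removes stable differences between sites and shifts common to all sites. It does not remove a change in patient mix confined to the intervention ED, and with one intervention hospital such a change cannot be separated from the intervention unless the model measures it. Ambulance arrival, as listed, does not separate transport from the scene from transport between hospitals.

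The other planned safeguards do not close the gap. The SAP itself notes that the parallel-trends test considers only the pre-implementation phase, so it cannot see a change between phases. In the interrupted time series, a step change in transfer share at the intervention ED would load on the same intervention-by-period term that is read as the effect. The models for mortality, length of stay and charges use the same covariate list and share the gap.

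**Working it through.** **Stated power.** Inputs from SAP, Power: SD 75 minutes; 1,650 intervention and 2,200 control sepsis patients a year; 90% power for 16 minutes. Alpha is 0.05 (SAP, Data analysis), taken as two-sided.

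- Closed-form SE of β3 with one year per phase = 75 × √(2/1650 + 2/2200) = 75 × 0.04606 = 3.45 minutes.
- Power at 16 minutes = Φ(16/3.45 − 1.96) = 99.6%.
- SE implied by the stated 90% = 16/(1.960 + 1.282) = 4.94 minutes.

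The stated 90% is not reproduced. It came from simulations whose details are not given, and it errs on the cautious side. The documents state no SE, so both values are carried below.

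**Bias.** Bias = (change in transfer share at the intervention ED − change at the controls) × (mean difference in door-to-antibiotic time, transfer versus direct arrival, left after adjustment).

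Neither factor is in the documents. Assumed ranges are a differential shift of 3 to 8 percentage points and a residual gap of 30 to 90 minutes. False-positive rate with no true effect = P(|Z + bias/SE| > 1.96).

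| Shift × gap | Bias (min) | Share of 16 min | Rate, SE 4.94 | Rate, SE 3.45 |
|---|---|---|---|---|
| 0.03 × 30 | 0.9 | 6% | about 5% | about 6% |
| 0.05 × 60 | 3.0 | 19% | about 9% | about 14% |
| 0.08 × 90 | 7.2 | 45% | about 31% | about 55% |

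For the middle row, z = 3.0/4.94 = 0.61 or 3.0/3.45 = 0.87.

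**Does ambulance arrival absorb it?** This was checked with a linear difference-in-differences simulation at the planned sample sizes. Assumed inputs: transfers are 15% of intervention-ED sepsis patients before and 10% after, and 5% at the controls throughout. The gap is 60 minutes in either direction. Ambulance arrival is 95% in transfers and 45% in others, with a 20-minute effect of its own.

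- With ambulance arrival adjusted, the absolute bias is about 2.8 minutes. After adding a transfer indicator it is about 0.
- With a 10-point fall, it is about 5.6 minutes, then about 0.
- With the same fall at the controls (same 15% starting share), it is about 0 without any indicator.

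The simulation did not include APS, SOFA or systolic pressure, and it used a linear rather than a gamma model. It shows that ambulance arrival alone is a weak proxy under these inputs. It does not show what remains under the full covariate set.

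**The case against.** Several points on the other side stand.

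- Both controls are referral hospitals, and phase #3 covers the same calendar year at all three sites. Only a shift that differs between them matters, and no document reports a change in transfers anywhere. The referrals mentioned in Protocol 4.1 describe the population served, not sepsis transfers through the ED.
- Entry to the primary cohort requires an eligible antibiotic and a culture in the study ED itself. A patient treated and cultured elsewhere enters only if both are repeated, which limits the transfer share.
- APS, SOFA, systolic pressure and the other covariates may absorb part of any transfer effect.
- One planned sensitivity analysis uses antibiotic-treated patients in the high-risk cohort, which does exclude recent prior antibiotics. That is a different population, however, and it keeps transfers not treated within the 6 hours before arrival, so it cannot isolate the question.
- A list of data elements is not a promise to model each one, and the covariates were chosen through a prespecified graph. Even so, transfer plausibly meets the SAP's own rule, and the plan already treats long-term-care origin and arrival mode as relevant.

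A reader might infer that `snf` is a yes/no recode of source of admission and should be replaced by it. The documents do not say so. Protocol 6.5 gives address as the means of identifying nursing-facility residence, and a resident of such a facility can also arrive from another hospital. Replacing `snf` could misclassify those patients and lose a covariate that the graph supports.

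**Conclusion.** The gap is real but conditional. The variable is collected, and no primary or secondary model, fallback weight, listed sensitivity analysis or primary-cohort rule deals with transfers. Bias follows only if the transfer share changes differently at the intervention ED and transfer still predicts the outcome after adjustment.

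Two stronger readings are tempting and unsupported. One is that the primary estimate is biased, or that transfer patterns at the intervention ED did change; the documents give no transfer share, shift or time gap, so even the sign is unknown. The other is to treat 3.45 minutes as the planned standard error and quote only the 14% and 55% error rates. The stated 90% power implies 4.94, for which the figures are about 9% and 31%.

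Under the middle assumption (5 points, 60 minutes) the bias is 3 minutes, about a fifth of the 16-minute target. The point is worth acting on because the remedy is nearly free and prespecifying it avoids a post hoc choice. It does not undermine the design.

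**What to change.** 1. Keep `snf`. Add a binary outside-hospital transfer indicator, taken from the collected source-of-admission variable, to the SAP's primary and secondary covariate list and to the fallback propensity covariates for sepsis cohorts. State that it records the origin of the ED arrival, since Protocol 6.5 does not say so, and that it may overlap with `snf`.
2. Report the transfer share among sepsis patients by site and phase, so that a reader can see whether a differential shift occurred.
3. Add one sensitivity analysis of the primary outcome that leaves out outside-hospital transfers.

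The cost is SAP wording, one table row and one extra model run. No new data collection is needed, and the primary model gains one parameter with about 2 × (1,650 + 2,200) = 7,700 patients.
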